## **E.7 Patient Safety Monitoring**

A data safety monitor will be appointed for this study. This person will otherwise be uninvolved in the planning or execution of this trial but will have the ability to unblind the collected data to analyze and determine if subjects experiencing an unacceptably high level of adverse events. The adverse effects of Botox are typically mild, transient, and well tolerated by most patients. Additionally, most side effects of Botox are commonly seen at baseline in the trauma population being studied (ex: generalized weakness, constipation, difficulty with urination, etc). For this reason, only adverse events outside of what would reasonably be expected for a typical post-operative trauma patient will be considered. These adverse events will be assessed by the treating physicians at every follow-up appointment (2 weeks, 6 weeks, 3 months, and 6 months), who will notify the data safety monitor within 24 hours. If deemed necessary, the data safety monitor will unblind the collected data and determine if the study group is experiencing adverse events at a significantly higher rate or with greater severity than the control group. If the risk to patients is deemed unacceptably high by the data safety monitor, the study will be terminated and the results will be published.

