All patients will be treated by a fellowship trained orthopaedic surgeon who has completed advanced training in either trauma or foot and ankle surgery. Patients will all undergo a staged fixation approach which involves primary external fixation with irrigation and debridement if necessary, followed by open reduction and internal fixation when soft tissues allow. Additional procedures on the injured extremity that take place between external fixation and definitive fixation (ex: ORIF of the fibula or repeat irrigation and debridement) do not disqualify the patient from the study as long as definitive fixation takes place within 3 weeks (21 days) of the injury. All definitive operations will take place at either Carolinas Medical Center – Main, or Carolinas Medical Center – Mercy.

At the time of definitive fixation, the hospital's investigational pharmacy will provide a blinded solution of either Botulinum toxin A or 0.9% sodium chloride solution for injection intraoperatively following skin closure. Four syringes containing 0.5 ml 0.9% sodium chloride, with or without Botulinum toxin type A based on the patient's randomization, will be provided and refrigerated until they are ready to be administered. Both the physician and the patient will be blinded to the contents of the syringe. Once reconstituted, botulinum toxin type A will only last for 4 hours at room temperature so it will be necessary to not allow the solution to sit at room temperature for an extended period of time. All patients in the study group will receive onabotulinumtoxinA, Botox® (Allergan, Irvine, California) provided by the investigational pharmacy. The total dose of botulinum toxin will be calculated based on the patient's weight in kilograms, such that a total dose of 200U of Botox will be used for a 70 kg individual (see Table 1 below). The dosage will scale linearly in

proportion to the patient's body weight, such that each kilogram change results in a 3U change in Botox (rounded to the nearest 30U interval change from 200U, with a maximum of 300U). This dosing regimen was chosen based on the effective dose for an average gastrocnemius from other studies.

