**Table 1: Botox Dosing by Weight**

45-55 kg:	140 U
55-65 kg:	170 U
65-75 kg:	200 U
75-85 kg:	230 U
85-95 kg:	260 U
95-105 kg:	290 U
105-115 kg:	300 U

At the completion of surgery, the gastrocsoleus complex will be injected in four locations (superior medial, superior lateral, inferior medial, and inferior lateral) prior to the application of short leg splint, per the recommendation of prior studies. At each injection site,  $\frac{1}{4}$  of the total dose of botulinum toxin A or normal saline will administered in approximately 0.5 ml injections. The use of EMG or other imaging modalities has been recommended to ensure accuracy of botulinum toxin injection at the target muscle motor end plates, however it is not necessary when injecting the gastrocsoleus complex, even in small children due to its large size and superficial location. The injection sites are illustrated in the figure 2 below:

[figure not shown]

Figure 2

Following definitive fixation and study injections, patients will be placed in a well-padded splint in at least neutral dorsiflexion for two weeks to allow for wound healing. Following wound healing, patients will transition to a removable orthosis and begin range of motion exercises and stretching techniques. All patients will undergo a structured exercise regimen. Each patient will receive a pamphlet at an 8th grade reading level containing a standardized exercise protocol which clearly states the exercises to be utilized, the frequency, and duration. As long as there are no adverse events, patients will proceed to touch down weight bearing at roughly 6 weeks postoperatively and continue their exercise program. Patients will then advance to partial weight bearing at approximately eight weeks and full weight bearing as tolerated at 10 to 12 weeks, as long as no adverse events occur precluding this progression.

Study participants will return to regularly scheduled follow-up appointments to monitor their progress. At each follow-up appointment (2 weeks, 6 weeks, 12 weeks, 6 months, and 1 year), patients will be monitored for signs and symptoms of Botox toxicity. All patients will be seen in follow-up at one of two clinic locations. At each site, research staff familiar with the study will be present along with a device for measuring dorsiflexion in a standardized fashion.

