##### **5.6.a.1 Botulinum Toxin Safety**

Botulinum Toxin A has been approved by the FDA for more than 20 years and has a long-established safety profile. When used correctly, the side effects of Botulinum Toxin type A injections are uncommon and usually mild and transient. Local side effects are the most common and are usually mild pain at the injection site and adjacent muscle weakness due to diffusion of the toxin across fascial barriers. Systemic side effects are very rare and include mild generalized weakness, urinary incontinence, constipation, and dysphagia; all of which are typically seen in susceptible individuals. Botox is contraindicated in patients with a history of neuromuscular disorder such as myasthenia gravis, and in patients receiving aminoglycoside antibiotics or non-depolarizing neuromuscular blocking agents, as these can all potentiate the effects of the toxin. It is also relatively contraindicated in patients with a history of pseudobulbar palsy and frequent chest infections for concern over aspiration pneumonia, an exceedingly rare, but serious side effect. These adverse events are not expected to cause problems based on our study design and patient population.

Of the local side effects, pain at the injection site is unlikely to be noticed by the patient as injections will be administered under general anesthesia and the patient's co-committent injury will likely dwarf any residual pain from the injection. The diffusion of Botox into adjacent muscle groups is not only inconsequential, but in-fact desired based on our study design. Although all injections will be made in the muscle belly of the gastrocnemius, diffusion into the deeper soleus muscle would provide additional weakness of the gastrosoleus complex and potentially result in better outcomes without causing additional functional impairment

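### The safety-monitoring section's expectedness limit may keep ordinary-severity weakness and constipation, two of the four systemic toxin effects the protocol names, out of the monitor's comparison by arm

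*Combined protocol and SAP*

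**What the plan says.** Section E.7 (Patient Safety Monitoring) starts from the observation that "most side effects of Botox are commonly seen at baseline in the trauma population being studied (ex: generalized weakness, constipation, difficulty with urination, etc". From this it concludes that "only adverse events outside of what would reasonably be expected for a typical post-operative trauma patient will be considered". The next sentence refers back to that restricted set: "These adverse events will be assessed by the treating physicians at every follow-up appointment (2 weeks, 6 weeks, 3 months, and 6 months". The treating physicians then notify the monitor within 24 hours. If the monitor thinks it necessary, the collected data are unblinded to "determine if the study group is experiencing adverse events at a significantly higher rate or with greater severity than the control group", and the study can be terminated on the result.

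The Botulinum Toxin Safety section (headed 5.6.a.1, within E.6) lists the systemic effects: "Systemic side effects are very rare and include mild generalized weakness, urinary incontinence, constipation, and dysphagia". It also says that "the side effects of Botulinum Toxin type A injections are uncommon and usually mild and transient". It gives no rates.

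Section D.3 provides a blinded saline control: "Both the physician and the patient will be blinded to the contents of the syringe". The text after the dosing table in D.3 adds a separate monitoring statement without the E.7 limit: "At each follow-up appointment (2 weeks, 6 weeks, 12 weeks, 6 months, and 1 year), patients will be monitored for signs and symptoms" of toxicity. It does not say what is written down or who receives it.

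**The concern.** When a drug effect resembles the ordinary course of recovery, a physician looking at one blinded patient cannot say which it is. A concurrent randomised control helps because it shows how often the symptom occurs without the drug. E.7 takes the overlap with background as a reason to set such events aside before the arms are compared, which leaves that information unused for the effects where it is most relevant. Since the protocol expects side effects to be mostly mild, ordinary severity is also where most cases would fall.

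At stake is the completeness of the safety record by arm. The monitor's judgement of whether risk is acceptable may rest on it. Under D.8 the pilot data join the full cohort if the protocol is unchanged, so a gap in recording now would carry forward, and mild transient symptoms are hard to recover later.

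**Working it through.** The plan states no figure on this point to reproduce, so the first three steps compare texts. The fourth asks how much recording could show at this sample size.

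**1. Matching the two lists.**

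| Systemic effect (Botulinum Toxin Safety) | Among E.7's examples of background symptoms? |
|---|---|
| Generalized weakness | Yes |
| Constipation | Yes |
| Urinary incontinence | Related term only (difficulty with urination) |
| Dysphagia | No |

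Direct matches: 2 of 4, or 3 of 4 if the urinary terms are taken as one. E.7's examples are left open-ended. The safety section adds that dysphagia may be a local effect and is unlikely with this injection site.

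**2. Following the path to the monitor.** E.7 restricts the events considered; the restricted events are what physicians assess and notify; the monitor may then compare arms. Whether an event is outside expectation is a clinical judgement, so unusually severe or late cases may pass. Ordinary cases of the matching effects may not.

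**3. Looking for another route.**
- D.2, Complications: ten items, captured at each office visit. None names any of the four effects (0 of 10). Rehospitalizations is one of the ten and has no expectedness limit, so cases serious enough for readmission would be captured.
- D.3: toxicity signs are monitored at each visit, with no stated record or recipient.
- D.4, Data Analysis: covers the primary and secondary outcomes and also compares the arms on compliance, time to full weight bearing and return to work. It names no adverse-event analysis.
- E.7, collected data: undefined. It could be broader than the notified events, but no section says that expected-type events are collected.
- Visit lists: D.3 has five visits and E.7 has four (12 weeks and 3 months taken as the same visit). They differ only at 1 year.

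**4. What recording could show with 10 per arm.** Exact (Clopper-Pearson) 95% intervals: 0/10 gives an upper limit of 1 − 0.025^(1/10) = 30.8%, so 0 to 30.8%; 1/10 gives 0.3 to 44.5%.

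The documents give no rates, so I assumed independent binomial counts, X ~ Bin(10, b + e) on Botox and Y ~ Bin(10, b) on saline, with background b of 20, 30 or 50% and excess e of 0, 1 or 2 percentage points. The small excess reflects the protocol's description of systemic effects as very rare. Expected extra Botox patients: 10 × 0.01 = 0.1 to 10 × 0.02 = 0.2. P(X > Y) is the sum of P(X = x)·P(Y = y) over x > y. The Fisher column adds the condition that the two-sided p is below 0.05.

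| Excess | P(X > Y), b = 20 / 30 / 50% | P(X > Y and Fisher p<0.05), b = 20 / 30 / 50% |
|---|---|---|
| 0 | 0.388 / 0.403 / 0.412 | 0.004 / 0.006 / 0.006 |
| 1 point | 0.411 / 0.423 / 0.430 | 0.005 / 0.007 / 0.007 |
| 2 points | 0.434 / 0.443 / 0.447 | 0.006 / 0.008 / 0.008 |

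More affected patients on Botox than on saline would be seen in 41 to 45% of trials with such an excess, against 39 to 41% with none. The significance test would be positive in under 1% either way.

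**The case against.** The strongest reply has four parts.

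First, E.7 limits which events are considered; it does not say that others go unrecorded. The monitor unblinds the collected data, which E.7 leaves undefined, and D.3 looks for toxicity signs without the limit. A reader might infer that ordinary cases are certain never to reach the monitor. The documents do not support that. What stands is that they may not, because no section requires them to be recorded or passed on.

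Second, D.3 and E.7 need not contradict each other on scope: broad observation in clinic with narrower escalation is a workable arrangement. I accept this. The defect is the missing link between the two. The visit-list difference should be reconciled but matters little here, since it falls at 1 year and E.6.a.2 says the paralysis improves over an average of 2 to 4 months.

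Third, serious cases have other routes: the severity judgement and the rehospitalization item. This is right, and it confines the point to ordinary cases.

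Fourth, with 10 per arm the record would seldom distinguish the arms. A reader might infer that the saline arm would reveal a toxin excess if only the events were logged. The calculation above does not support that for a small excess. The case for recording rests on description and on carrying data into the full trial, in a pilot whose stated purpose is to test procedures and collect preliminary data.

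**Conclusion.** The point holds as a gap in the safety record and should be fixed. E.7 states its restriction and gives the toxin's own side effects as the reason for it. Two of the four named systemic effects are directly affected, possibly three, and only at ordinary severity. No other section clearly restores them to the comparison by arm.

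It would be wrong to read this as a finding that toxin harm will be missed, or that the trial would detect it under a different rule. The documents establish neither. The textual conclusion rests on reading E.7's reference to these adverse events as the restricted set, which is the natural reading. The quantitative limits rest on the assumed 20 to 50% background and 1 to 2 point excess; a larger excess would be easier to see. Confidence is moderate, mainly because the collected data are not defined.

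**What to change.** - At the visits already scheduled, record generalized weakness, urinary symptoms, constipation and dysphagia, with severity, in every patient whether or not the symptom is expected.
- Give the monitor descriptive patient-level counts by arm with exact confidence intervals. Section D.3 randomises each limb separately in bilateral patients, so a systemic symptom in a patient with one Botox and one saline limb belongs to neither arm; list any such patient separately.
- Apply the expectedness criterion in E.7 only to the 24-hour notice.
- State in D.3 what the toxicity monitoring records and that it goes to the monitor, define the collected data in E.7, and reconcile the visit lists of D.3 and E.7.

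Cost: with five visits, 20 patients × 5 visits × 4 items = at most 400 checklist entries (20 × 4 × 4 = 320 with four visits), plus short wording changes. The drawback is more minor events to log, with counts that remain descriptive at this size.

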#### **D.4 Data Management**

All data will be entered into REDCap, a web-based data entry and management system that provides logic checks on input and checks for invalid entries. Data will be entered continuously as they are collected and stored in univariate form. We will also run standard checks for outliers, duplicates and other types of errors which may occur within a complex data file. All data files will be password protected and hard copies of blinded patient records will be maintained in locked cabinets in the research office.

*Data Analysis:* In order to determine that the randomization process produced comparable groups, we will use t-tests and cross-tabulations to compare patients in the treatment group to patients in the placebo group on the following variables: age, race, gender, BMI comorbidities, fracture classification, time until definitive fixation, tobacco use, workers compensation status, level of education, marital status, personal income, health insurance, working status before surgery, compliance with weight-bearing restrictions, compliance with prescribed treatment, time until full weight bearing and return to work.

Analyses will follow the intent-to-treat paradigm, under which all patients will be analyzed according to the treatment group to which they were randomized. Intention to treat analyses of outcomes will be conducted in two stages. First, we will conduct a bivariate analysis to examine relationships between assigned treatment

group, primary and secondary outcomes, and potential covariates and confounders (demographics, injury characteristics, co-morbidities). We will then use the results to build a multivariate model to predict primary and secondary outcomes based on treatment type.

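### The safety monitor is sent only events unexpected after trauma surgery, so ordinary cases of the toxin's known systemic effects may never be compared with saline

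*Combined protocol and SAP*

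**What the plan says.** E.7 (Patient Safety Monitoring) observes that "most side effects of Botox are commonly seen at baseline in the trauma population being studied (ex: generalized weakness, constipation, difficulty with urination, etc". For that reason, it continues, "only adverse events outside of what would reasonably be expected for a typical post-operative trauma patient will be considered". The next sentence ties reporting to this filtered set: "These adverse events will be assessed by the treating physicians at every follow-up appointment", and the physicians notify the data safety monitor within 24 hours. If the monitor thinks it necessary, the collected data are unblinded to "determine if the study group is experiencing adverse events at a significantly higher rate or with greater severity than the control group".

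The section on botulinum toxin safety (within E.6) describes the drug's systemic profile: "Systemic side effects are very rare and include mild generalized weakness, urinary incontinence, constipation, and dysphagia". D.3 (Methods) says of the syringe that "Both the physician and the patient will be blinded to the contents of the syringe". After Table 1, D.3 also says that at each follow-up visit (2 weeks, 6 weeks, 12 weeks, 6 months and 1 year) "patients will be monitored for signs and symptoms of Botox toxicity". D.4 (Data Management) adds: "All data will be entered into REDCap".

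**The concern.** Two of the four systemic effects in the toxin safety section, generalized weakness and constipation, are the same complaints that E.7 cites as ordinary in trauma patients. A third is related: E.7 names difficulty with urination, the safety section urinary incontinence. So the reason given for the filter is that the drug's own known effects look like background.

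In that situation a judgement on one blinded patient cannot work, because constipation from the toxin and constipation after trauma surgery look alike. A count against saline can help, since the randomized control arm supplies the background rate. E.7 gives the monitor that comparison to make, but removes events judged ordinary before it can be made.

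At stake is how the pilot's safety result is read. Few or no reports of these symptoms in either arm could be taken as evidence of tolerability when the symptoms were never compared. D.5 runs the pilot in the same manner as the full trial, and D.8 would pool its data with the full cohort if the protocol does not change, so symptoms left unrecorded now may be unrecoverable later.

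**Working it through.** **Step 1: can an ordinary case reach the comparison by another route?**

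| Place | What it provides | Does it close the gap? |
|---|---|---|
| D.2, Complications | Bone union, infection, wound and skin problems, further surgery, rehospitalizations | No systemic toxin effect listed |
| D.3, after Table 1 | Toxicity check at five visits, with no expectedness limit | No items, grading, recording rule, route to the monitor or tabulation |
| End of D.3 | Comparison by arm of dorsiflexion and of the share reaching 10 degrees | No adverse events |
| D.4 | All data go into the database; baseline, compliance and recovery variables compared by arm; outcome models | Covers what is collected, but does not say these symptoms are; no adverse-event analysis |
| E.7 | Monitor may unblind the collected data if necessary | Includes these symptoms only if they were recorded; the only stated alert is the filtered notice |

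No section guarantees the route, and none rules it out.

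**Step 2: illustration of size.** The plan states no safety event rate, threshold or power, so there is no figure of its own to reproduce. The one input from the documents is 10 patients per arm. Assumed inputs are the saline rate p0, the toxin rate p1, and the share q of affected patients who pass the filter (q = 1 means no filter). Patients are treated as independent.

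With A affected patients counted on saline and B on toxin,

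A ~ Binomial(10, q·p0), B ~ Binomial(10, q·p1), and P(B − A ≥ 3) = Σ P(A = a)·P(B = b) over all pairs with b − a ≥ 3.

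Three extra patients stands for a visible imbalance. It is not a rule in the plan.

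| p0 v p1 | q = 1 | q = 0.5 | q = 0.25 |
|---|---|---|---|
| 5% v 10% | 0.046 | 0.009 | 0.0015 |
| 10% v 20% | 0.166 | 0.046 | 0.009 |
| 30% v 40% | 0.241 | 0.115 | 0.037 |
| 10% v 30% | 0.383 | 0.124 | 0.027 |
| 30% v 50% | 0.413 | 0.196 | 0.066 |
| 10% v 40% | 0.611 | 0.234 | 0.057 |
| 30% v 60% | 0.601 | 0.291 | 0.102 |
| No difference, 10% | 0.030 | 0.007 | 0.001 |
| No difference, 30% | 0.110 | 0.056 | 0.017 |
| No difference, 50% | 0.132 | 0.096 | 0.043 |

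**Step 3: smaller excesses, closer to the protocol's description.** With no filter and an excess of 1 to 2 points, the chance is 3.8% to 4.8% from a 10% background (3.0% with no true difference) and 12.1% to 13.2% from a 30% background (11.0% with no true difference).

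**Step 4: formal testing.** The two-sided Fisher exact test at 0.05 with every event counted has power of about 6% at 10% v 30%, 13% at 20% v 50% and 43% at 30% v 80%. A p-value threshold would therefore miss most of even these large excesses.

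**Step 5: chance imbalances after the fix.** At 30% in both arms the chance is 0.110 per symptom. For at least one of three symptoms, assumed independent, it is 1 − (1 − 0.110)³ ≈ 0.29.

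**The case against.** The strongest reply is that E.7 limits what is considered and notified, not what is observed. D.3 checks every patient for toxicity without an expectedness limit, the data go into a database, and the monitor may unblind what was collected. On that reading the filter governs the 24-hour notice and little else. This stands in part: a reader might infer that the plan collects no toxicity information, or that it bars all toxin effects from the comparison, and the documents support neither. What remains is that no section says how the D.3 observations are recorded, sent on or compared.

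Second, expectedness depends on circumstances. Weakness or constipation that is unusually severe, starts late or persists to 6 or 12 weeks could reasonably be judged unexpected and reported. Dysphagia is not among E.7's examples of ordinary events. This stands, and it means that no constant pass-through share can be defended; the values 0.5 and 0.25 are illustrations.

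Third, the protocol calls systemic effects very rare and keeps the dose well below its stated maximum of 12 U/kg. By Table 1 the highest two-leg dose is 2 × 140 U / 45 kg = 6.2 U/kg. Excesses of 20 to 30 points fit poorly with that description. This also stands. It limits the expected yield of the change, but does not explain why the comparison should go unmade in an off-label use with a saline control.

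Finally, this is a reasoned choice in a 20-patient pilot with an independent monitor. The reason given, background noise, justifies filtering urgent notices. It does not justify filtering the count.

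**Conclusion.** The point holds as a cheap improvement to safety assessment. E.7 states a rule that can keep ordinary cases of generalized weakness, constipation and urinary symptoms from the comparison with saline, and no other section guarantees another route. This rests on the text and needs none of the assumed rates.

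The size is unknown. If a quarter of affected patients passed the filter, the chance of seeing at least 3 more on toxin would fall from between 5% and 61% to between 0.1% and 10% across the excesses examined, all of them assumed. With only 10 per arm, even complete recording gives a visible comparison and not reliable detection.

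A reader might go further and infer that the filter hides a real harm, or that full recording would reveal one. The documents support neither: they give no event rates, and for small excesses the full table barely differs from chance. The efficacy aims are not affected.

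**What to change.** 1. In E.7, apply the expectedness test only to the 24-hour notice.
2. At the visits already listed in D.3, record presence and grade of generalized weakness, constipation, urinary symptoms and dysphagia for every patient, expected or not. The visits through 12 weeks matter most, because E.6.a.2 puts recovery from the paralysis at an average of 2 to 4 months; later forms would mostly add background.
3. Give the monitor the counts and grades by arm. State that saline serves as background and that no p-value threshold applies.
4. List patients with two randomized legs (D.3) separately, with their exposure. Do not pool them into the toxin column: if legs were allocated independently 1:1, an either-leg rule would put 1 − 0.5² = 75% of such patients there (blocking may change the share).

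Cost: a four-item form at existing visits, with no added visits. For 20 patients that is 20 × 5 = 100 forms, of which 20 × 3 = 60 fall by 12 weeks. The monitor has more background events to read and will meet chance imbalances: at an assumed 30% in both arms, about 11% per symptom and about 29% for at least one of three independent symptoms. Weighing counts together with severity keeps such an imbalance from acting as a stopping trigger.
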